Official title of the study

**A Multilevel CBPR Intervention to Improve
Colorectal Cancer Screening in Underserved
Vietnamese Americans**

NCT number: NCT03413605

Date of the study protocol with SAP: May 8, 2020

1) Abstract of the study

Colorectal cancer (CRC) is the second most commonly diagnosed cancer and the third highest cause of mortality in Vietnamese and Asian Americans. CRC incidence is rising rapidly in Vietnamese Americans, but they have among the lowest rates of CRC screening (14%) and are more likely to be diagnosed with advanced stage disease, which is highly preventable. Over 85% of Vietnamese Americans in our region (PA, NJ and NYC) are foreign-born with limited English proficiency, have low SES, and live in economically disadvantaged neighborhoods. Many lack knowledge about CRC risks and screening benefits, and have limited access to culturally appropriate preventive care. Center for Asian Health, Temple University will be working with Vietnamese CBOs to address their critical health disparities. **Specific Aim** is to test the hypothesis that the proposed multilevel CRC intervention will yield higher CRC screening rates compared to the control at 12-month follow up. This project represents the first large-scale community-based randomized controlled trial of a multilevel, culturally-appropriate intervention to increase CRC screening among underserved Vietnamese. If effective, this innovative CRC intervention can be used as a model program that has potential generalizability and sustainability in Asian American and other underserved ethnic communities to impact preventive behaviors at population level.

2) Objectives

The overall goal is to use a CBPR approach to collaborate with Vietnamese CBO partners to increase CRC screening by reducing multilevel healthcare access barriers for underserved Vietnamese Americans.

The purpose of the study is to determine the effectiveness of a multilevel, theory- and evidence-based CBPR intervention to increase CRC screening in underserved Vietnamese. The proposed multilevel CRC intervention will be guided by Social Ecological Model that addresses sociocultural, behavioral and environmental determinants and intervention strategies at individual, interpersonal, and community organizational levels for obtaining CRC screening.

Specific Aims: Aim 1 is to test the hypothesis that CPS + multilevel CRC intervention will yield higher CRC screening rates compared to CPS control at 12-month follow up; Aim 2 is to examine whether CPS + multilevel CRC intervention (which includes CHW-led group education, automated and interactive text messaging and phone-based peer support) is more effective in changing screening determinants (e.g. KAB, self-efficacy, risk factors, lifestyles, social support, social norms, access barriers) than CPS control condition.

It is hypothesized that the multilevel CRC intervention will yield higher CRC screening rates compared to CPS control at 12-month follow up.

3) Resources and Setting

Protocol Template for Minimal Risk Studies not Regulated by FDA

All key personal involved in this study were trained for this protocol, have meetings regarding the materials development, timeline and process of this study to ensure that all key personals were on the same page along with the study progress. The study PI and senior key staff members will provide detailed training about the study to all personal involved in this study including project coordinator, community health workers, collaborating community leaders and designated staff from collaborating partners.

The study will be conducted in greater Philadelphia area including (south NJ, DE and PA areas) and New York City with our long collaborating community partners. All participants in the described study will be identified and recruited by collaborating community partners, and consented by trained team staff of Center for Asian Health, Temple University.

4) Study Design

a) Recruitment Methods

In total, 900 participants will be recruited, including:

- 800 study participants
- 40 CBO leaders/staff from 20 collaborating CBO partners
- 60 family members or close friends of study participants.

The research team will recruit subjects after the TU IRB office approves the protocol.

Participants will be recruited through collaboration with Vietnamese community-based organization partners located in greater Philadelphia area including (south NJ, DE and PA areas) and New York City. Over the past 16 years, the Center for Asian Health has established solid collaboration relationships with these partners. In this study's recruitment effort, the Center has received collaboration commitment from the community leaders during grant proposal development stage. Planning meeting will be conducted with collaborating community leaders.

A total of \$45 incentive for completing all survey forms before and after workshop and the telephone interview (or in-person survey form collection) at 12-month after the workshop (*additional \$20 incentive will be provided for completing the expanded 12-month follow up survey form*).

b) Inclusion and Exclusion Criteria

Inclusion Criteria:

- Study participants (N=800) will be included in the study if they meet the following criteria:

1) self-identified Vietnamese ethnicity, 2) age 50 and above, 3) accessible by cell telephone, 4) presence in the same geographic study area for a period of one year

Protocol Template for Minimal Risk Studies not Regulated by FDA

(to minimize participant attrition); 5) not enrolled in any CRC intervention (to prevent a potential program impact), 6) do not have colorectal polyp, CRC cancer or a family history of CRC (first degree relative). The guidelines recommended by American Cancer Society will be used to determine participants' screening eligibility: No FIT in past year or no sigmoidoscopy in past 5 years, no double-contrast barium enema in the past 5 years, or no colonoscopy within the past 10 years

- CBO leaders/staff (n=40) will be included in the study if they meet the following criteria: 1) Self-identified Vietnamese ethnicity, 2) CBO leader involved in the study, 3) Accessible by telephone or cell telephone.
- Family members or close friends of study participants (n=60) will be included in the study if they self-identified as a family member or a close friend of the study participant, who provided help to study participant during his/her health care activities.

c) Study Procedures, Method, and Data Analysis Plan

Research design/method- This is a 2-arm randomized controlled trial with baseline, post-education test and 12-month assessments. Collaborating Viet community partners will be randomly assigned into either intervention group, or comparison group; participants enrolled from each participating community partner will be automatically assigned to their CBO study group: intervention or comparison.

Group education workshops will be arranged in working collaborating community partners. The education session is a curriculum-based group education; each group will be having about 15-20 participants. All group education sessions will take place at collaborating Viet community partners' sites, and delivered in Vietnamese language, with offering of refreshment. We will allow 5-7 minutes for participants to get to know each other and to get comfortable talking to the group.

In addition to information collection from study participants, we will conduct telephone interview with 40 leaders/staff from 20 collaborating CBO partners (2 persons per partner site) to gain feedback about the intervention when field research activities is completed.

Feedback about the intervention will also be gathered from 60 family members (or close friends) of 60 study participants.

For data analysis approach, first, we will perform analysis using Viet community organization as unit of analysis. For testing main null hypothesis of no difference in primary endpoint (conversion to screening compliant) and secondary endpoints, we will use randomization tests with a randomization distribution in accord with stratified randomization of the experimental design. Second, we will also perform statistical analyses using individual as unit of analysis. For these analyses, we will use the generalized linear mixed models for the regression analysis of correlated binary response data with covariates specific to the individual.

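### Never-screened and previously screened but overdue people can both enter, but the main CBO-level test names no baseline covariate; adjusting for screening history is a cheap gain in precision

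*Combined protocol and SAP*

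**What the plan says.** Section 4(b), Inclusion and Exclusion Criteria, defines eligibility by look-back windows: "The guidelines recommended by American Cancer Society will be used to determine participants' screening eligibility: No FIT in past year", with further windows of 5 years for sigmoidoscopy and barium enema, and "or no colonoscopy within the past 10 years". It does not require that a person has never been screened, and it sets no minimum time overdue.

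Section 4(a) gives "800 study participants" and "40 CBO leaders/staff from 20 collaborating CBO partners". Section 4(c) randomizes the partners, and "participants enrolled from each participating community partner will be automatically assigned to their CBO study group: intervention or comparison".

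Section 4(c) then lists two analyses of the primary endpoint, conversion to screening compliant. The first takes the CBO as the unit: "we will use randomization tests with a randomization distribution in accord with stratified randomization of the experimental design". The strata and the test statistic are not named, and no covariate is mentioned. The second is an individual-level generalized linear mixed model with individual covariates, which are not listed. Prior screening is not named anywhere as a stratum, covariate or subgroup.

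**The concern.** The endpoint is a screening behaviour, so past screening behaviour is an obvious candidate predictor. A person never screened by any test and a person whose last FIT was 13 months ago both meet the entry rule. Their chance of converting within 12 months without intervention may well differ.

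Assignment is by CBO, and about 20 units are too few for randomization to balance the mix reliably in any one trial. If the share of previously screened people varies between CBOs, that variation enters the CBO-level conversion rates as noise and lowers power. A chance imbalance between arms would also stay in the raw estimate. One baseline item could remove much of this without giving up the chosen test.

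**Working it through.** **No figure to reproduce.** The plan states no power, effect size, alpha, intracluster correlation or dropout. Its counts are consistent: 800 + 40 + 60 = 900, and 20 × 2 = 40.

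**Inputs from the documents.** 800 participants and 20 CBOs, so 800/20 = 40 per CBO if spread evenly.

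**Assumed inputs.** All 20 CBOs are randomized 10:10 in equal sizes, with strata ignored. *s* is the mean previously screened share and σ its between-CBO SD. *p1* and *p0* are the 12-month conversion rates of previously screened and never-screened people, *d* = *p1* − *p0*, and τ is any further between-CBO SD. The documents give none of these.

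**Formulas**, with *m* = 40, *k* = 10 CBOs per arm and mean rate *p* = *p0* + *ds*:

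- Raw variance of a CBO rate: V_raw = d²σ² + [p(1 − p) − d²σ²]/m + τ²
- Variance after adjusting for individual history: V_adj = [s·p1(1 − p1) + (1 − s)·p0(1 − p0)]/m + τ²
- SE of the arm difference: √(2V/k)

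**Stronger case:** s = 0.35, σ = 0.15, 40% versus 10%, τ = 0.

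- p = 0.10 + 0.30 × 0.35 = 0.205; d²σ² = 0.09 × 0.0225 = 0.002025
- V_raw = 0.002025 + (0.162975 − 0.002025)/40 = 0.006049; SE = √(0.2 × 0.006049) = 0.0348
- V_adj = (0.35 × 0.24 + 0.65 × 0.09)/40 = 0.003563; SE = √(0.2 × 0.003563) = 0.0267
- Ratio 0.0267/0.0348 = 0.77. Simulation of this setting also gave 3.5 and 2.7 points.
- With τ = 0.05, add 0.0025 to each variance: SEs 0.0413 and 0.0348, ratio 0.84.

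**Weaker case:** s = 0.14, σ = 0.05, 30% versus 12%, τ = 0.05. The 14% is borrowed from the community screening rate in section 1, which is not a previously screened share among entrants.

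- p = 0.12 + 0.18 × 0.14 = 0.1452; d²σ² = 0.0324 × 0.0025 = 0.000081
- V_raw = 0.000081 + (0.124117 − 0.000081)/40 + 0.0025 = 0.005682; SE = 0.0337
- V_adj = (0.14 × 0.21 + 0.86 × 0.1056)/40 + 0.0025 = 0.005505; SE = 0.0332
- Ratio 0.98.

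**Chance imbalance, stronger case.** SD of the arm difference in share = √(0.2 × [0.0225 + (0.2275 − 0.0225)/40]) = 0.074. An imbalance of that size moves the raw difference by 0.074 × 0.30 = 0.022, or 2.2 points.

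**Does the adjusted test hold its level?** The test was simulated on residuals from the pooled conversion proportions by history. For one yes/no covariate these equal the fitted values of a logistic model without treatment. Settings: 20 × 40, 10:10, two-sided 0.05, 999 re-randomizations, 2000 runs, never-screened conversion 15%, residual CBO SD 0.3 and intervention effect 0.5 (both on the logit scale).

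| Share (SD) | Conversion if previously screened | Type I error, raw / adjusted | Power, raw / adjusted | SE under the null, raw / adjusted |
|---|---|---|---|---|
| 10% (0.05) | 30% | 0.037 / 0.046 | 0.53 / 0.57 | 0.0320 / 0.0318 |
| 20% (0.10) | 50% | 0.048 / 0.056 | 0.47 / 0.59 | 0.0399 / 0.0350 |
| 30% (0.15) | 50% | 0.044 / 0.052 | 0.42 / 0.59 | 0.0444 / 0.0363 |
| 30% (0.20) | 70% | 0.048 / 0.060 | 0.22 / 0.55 | 0.0622 / 0.0351 |

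Over all twelve settings run, type I error was 0.028 to 0.048 raw and 0.041 to 0.060 adjusted, and neither estimate was biased under the null. The raw test is slightly conservative because CBO counts tie. In the first row the SEs are almost equal, so that power gain is mostly tie-breaking, not precision. The last row is an extreme assumption.

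**The case against.** The strongest reply is that nothing here is an error. A randomization test that follows the design already carries chance imbalance in its null distribution, so it needs no covariate to be valid. That stands. A reader might infer that the main result would be biased or its error rate inflated; neither the documents nor the simulations support that.

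Other tempting readings also go too far:

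- *Overdue people would re-screen anyway.* The documents give no re-screening rate. One could argue the reverse, since missing an annual test already shows non-adherence.
- *The arms are known to differ at baseline.* No difference between CBOs or arms is reported. Only a possible mix among participants follows from the entry rule.
- *The plan ignores screening history.* The strata are unnamed and could include a screening-related factor, and the mixed model could include it as a covariate. What can be said is that neither is specified.
- *The information is already in hand.* A never-screened and an overdue person give the same answer to a look-back question such as no FIT in the past year, so eligibility alone need not separate them.

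The size is also open. With a low or even share the gain is small. When adjustment was made by regressing the 20 CBO rates on the CBO's share, the assumed setting of 14%, SD 0.05 and 30% versus 12% gave a variance ratio of 1.02, that is, no gain. The residual method avoids estimating a slope from 20 points, but its calculated gain in that setting is only about 2% of the SE.

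Finally, exactness of the adjusted test requires that the enrolled mix does not depend on arm. Partners identify and recruit participants (section 3), and the order of assignment and enrolment is not stated.

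**Conclusion.** The point holds as an efficiency improvement, not as a flaw in validity. The entry rule lets two groups in whose conversion may plausibly differ, and the main test, on about 20 clusters, specifies no adjustment for that difference. Under the assumptions shown, the adjusted-to-unadjusted SE ratio runs from about 0.98 to about 0.77, or 0.84 at the stronger end if CBOs also vary by a further 5 points; more extreme inputs give more. Where in this range the trial lies cannot be settled from the documents, because they give neither the previously screened share, nor its spread across CBOs, nor the conversion rates. The change is worth making because it is cheap, keeps the chosen test, and kept type I error near 0.05 in the simulations.

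**What to change.** 1. Record for every participant, at the eligibility check or baseline, *never screened* versus *previously screened but overdue*. Do this before the intervention starts and ideally before the CBO's arm is known.
2. Keep the stratified randomization test, but apply it to adjusted CBO values. Fit a logistic model of conversion on this variable, without treatment, over all participants. Take each CBO's observed minus expected conversion, and re-randomize arm labels within the design strata.
3. Enter the same variable in the individual-level mixed model.
4. Name the strata, the test statistic and the mixed-model covariates, and fix all of this before outcome data are examined.
5. State the order of CBO assignment and enrolment, and tabulate screening history by arm. Adjustment does not fully cure selective recruitment by partners who know their assignment, but the table would help show it.
6. Clarify how the screening windows in section 4(b) combine. Read literally, the alternatives could admit someone up to date by colonoscopy but without a recent FIT, which would widen the mix.

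Cost: possibly one added baseline question, one coded variable and a few lines of plan. The gain is negligible if history hardly predicts conversion.
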